15.4.3. Adverse Events of Special Interest

Pruritus: Treatment-emergent pruritus, defined as any preferred term including “Prur,” will be summarized separately by the MedDRA SOC, treatment group, and PT as a subset of all TEAEs. This summary will be repeated for patients with “new or worsened” pruritus events, as defined as follows:

- Mild, moderate, or severe treatment-emergent pruritus events in patients with no pruritus at Baseline, or
- Worsening of the severity of the Baseline condition in patients with pruritus at Baseline.

Baseline pruritus is defined as the investigator’s rating of severity as collected on the PBC Disease History eCRF. Patients whose Baseline severity is severe will be counted as worsening if an AE of pruritus with severe is recorded.

An analysis of treatment-emergent pruritus event days per patient years on study will be performed. The days at each severity grade, including the total days of event, the total patient years on study, and the event days per patient year on study at each severity grade, including the total, will be summarized. Each individual patient year on study will be derived as the last known date during the study minus the first dose date plus 1 divided by 365.25 days/year.

In order to explore the relationship between pruritus and the investigational product, the following time-to-event analyses will be performed:

- Time to first onset of treatment-emergent pruritus
 - The time to the start of the first episode will be calculated by date of onset of first episode – date of first dose of investigational product + 1.
 - Patients who never reported an AE of pruritus will be censored at the date of last contact.
- Time to onset of the first moderate or severe treatment-emergent pruritus
 - The time to the start of the first moderate or severe pruritus will be calculated by date of onset of the first moderate or severe pruritus – date of first dose of investigational product +1.
 - Patients who never reported a moderate or severe AE of pruritus will be censored at the date of completion or discontinuation.
- Time to onset of the first severe treatment-emergent pruritus
 - The time to the start of the first severe pruritus will be calculated by date of onset of the first severe pruritus – date of first dose of investigational product +1.
 - Patients who never reported a severe AE of pruritus will be censored at the date of completion or discontinuation.

The analysis of time to first onset of treatment-emergent pruritus AE, time to onset of the first moderate or severe treatment-emergent pruritus, and onset of the first severe treatment-emergent pruritus will include the number of patients with pruritus (first onset, first moderate or severe, first severe), the number of patients without pruritus (censored), and the minimum and maximum times in days. KM estimates will be calculated by treatment group. The tabulation will include the KM estimate methodology using 25th, 50th (median), and 75th percentiles of the medians and corresponding with associated 2-sided 95% confidence intervals (CIs), if the medians can be estimated as well as percentage of censored observations.

Fatigue: Treatment-emergent fatigue is defined as any preferred term which includes “Fatigue.” New or worsened treatment-emergent fatigue is defined as follows:

- Any mild, moderate, or severe treatment-emergent fatigue events in patients with no fatigue at Baseline, or
- Worsening of the severity of the Baseline condition in patients with fatigue at Baseline.

Baseline fatigue is defined as the Investigator’s rating of severity as collected on the PBC Disease History eCRF. Patients whose Baseline severity is severe will be counted as worsening if an AE of fatigue with severe is recorded.

An analysis of treatment-emergent fatigue event days per patient years on study will be performed. The days at each severity grade, including the total days of event, the total patient years on study, and the event days per patient year on study at each severity grade, including the total, will be summarized. Each individual patient year on study will be derived as the last known date during the study minus the first dose date plus 1 divided by 365.25 days/year.

In order to explore the relationship between fatigue and the investigational product, the following time-to-event analyses will be performed:

- Time to first onset of treatment-emergent fatigue
 - The time to the start of the first episode will be calculated by date of onset of first episode – date of first dose of investigational product + 1.
 - Patients who never reported an AE of fatigue will be censored at the date of last contact.
- Time to onset of the first moderate or severe treatment-emergent fatigue
 - The time to the start of the first moderate or severe fatigue will be calculated by date of onset of the first moderate or severe fatigue – date of first dose of investigational product +1.
 - Patients who never reported a moderate or severe AE of fatigue will be censored at the date of last contact.
- Time to onset of the first severe treatment-emergent fatigue
 - The time to the start of the first severe fatigue will be calculated by date of onset of the first severe fatigue – date of first dose of investigational product +1.

- Patients who never reported a severe AE of fatigue will be censored at the data of last contact.

The analysis of time to first onset of treatment-emergent fatigue AE, time to onset of the first moderate or severe treatment-emergent fatigue, and onset of the first severe treatment-emergent fatigue will include the number of patients with pruritus (first onset, first moderate or severe, first severe), the number of patients without fatigue (censored), and the minimum and maximum times in days. KM estimates will be calculated by treatment group. The quartiles, including the median time-to-event and their respective 2-sided 95% CIs, will be presented. KM estimates will be plotted as a “survival curve” for each treatment group.

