8.4.3. Other Reasons for Discontinuation of Study or Investigational Product

The following events are considered appropriate reasons for a patient to discontinue investigational product; however, these patients are expected to continue in the study until study termination (or at the discretion of the Sponsor):

- Patient begins treatment with commercially available OCA.

- The Investigator or Sponsor considers that it is advisable or in the best interest of the patient.
- The occurrence of clinical or laboratory AEs considered by the Investigator to be clinically important safety concerns and related to study drug.
- Withdrawal of consent
 - Consent may be fully withdrawn (in which case the patient discontinues both investigational product and study visits and procedures).
 - Consent may be modified to discontinue study visits but allow semi-annual telephone contact.
 - Consent may be modified to discontinue study visits or semi-annual telephone contact but allow continued access to medical records to assess for suspected major adverse cardiovascular events (MACE) and liver-related clinical events.
 - Early termination procedures should be conducted if the patient withdraws consent (see [Section 9.7.13](#)).

The Investigator is encouraged to contact the Sponsor prior to discontinuing a patient from treatment. The Investigator must notify the Sponsor study monitor by telephone or email as soon as possible if any patient prematurely withdraws from the study.

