13.1.1.3. Treatment-Emergent Adverse Event

A treatment-emergent AE (TEAE) is any event not present before the initiation of the investigational product or any event already present that worsens in either intensity or frequency following exposure to the investigational product.

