13.1.4. Reporting of Adverse Events and Serious Adverse Events

13.1.4.1. Reporting of Adverse Events

AE data will be collected from the time that signed informed consent is obtained until the patient fully completes her/his study participation of the study.

All AEs, whether believed by the Investigator to be related or unrelated to the investigational product, must be documented in the patient's medical records, in accordance with the Investigator's normal clinical practice and on the AE eCRF. Each AE is to be evaluated for duration, intensity, frequency, seriousness, outcome, other actions taken, and relationship to the investigational product. Redacted medical record source documentation will be requested for all SAEs and emergency room visits.

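### Section 15.4.3 gives only an on-study rate for pruritus and fatigue event-days, with no on-treatment rate beside it, and censors the six time-to-onset analyses by two different rules

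*Protocol*

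**What the plan says.** All references are to protocol Version 2, the current text.

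- **Denominator.** Section 15.4.3, pruritus: "Each individual patient year on study will be derived as the last known date during the study minus the first dose date"; one day is then added and the total converted to years of 365.25 days. The fatigue paragraph repeats the formula: "An analysis of treatment-emergent fatigue event days per patient years on study will be performed". No rate per time on treatment is specified.
- **Numerator.** Section 13.1.1.3 counts as treatment-emergent a new event or "any event already present that worsens in either intensity or frequency following exposure to the investigational product", and gives no closing date. Section 13.1.4.1 collects AEs "until the patient fully completes her/his study participation of the study", so events after the last dose are in the data.
- **Follow-up after stopping.** Section 8.4.3 lists, among the reasons to stop product while staying in the study, "Patient begins treatment with commercially available OCA". Sections 9.2.2 and 9.7.13 also expect such patients to continue. Section 7.1.3 puts the blinded period at about 3 years.
- **Censoring.** For any pruritus: "Patients who never reported an AE of pruritus will be censored at the date of last contact". For severe pruritus: "Patients who never reported a severe AE of pruritus will be censored at the date of completion or discontinuation"; moderate-or-severe pruritus has the same rule. All three fatigue endpoints are censored at last contact.

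**The concern.** Safety and tolerability against placebo is a primary objective (Section 6.1), and Section 5.5 names pruritus as the main adverse event related to OCA. Section 15.4 plans no formal safety test, so these descriptive rates and Kaplan-Meier summaries are the evidence that readers will use.

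As written, time after the last dose stays in the denominator and events in that time stay in the numerator, both under the randomized arm. Pruritus in a placebo patient who has moved to commercial OCA is placebo pruritus. Symptom-free time in an OCA patient who has stopped is OCA time. Section 15.4.3 says that the time-to-onset analyses are meant to explore the link between the symptom and the investigational product, yet four of the six follow patients past the end of dosing. The other two use a rule that can be read in two ways.

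**Working it through.** The protocol states no pruritus or fatigue rate and no safety effect size, so there is no figure of its own to reproduce. The check asks how much on-study averaging could dilute a difference.

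**Inputs from the protocol.** A 15% discontinuation rate (Section 15.2; period not stated, nor whether drug or study), 1:1 allocation, and blinded follow-up from 48 weeks to about 3 years.

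**Assumed.** The 15% means stopping product, in both arms, with follow-up continuing. Event-day rates on drug are r0 = 40 per patient-year on placebo and r1 = 80 on OCA (ratio 2.00, difference 40).

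**Step 1: off-drug share f of on-study time.**
- 15% in total, stops spread evenly over 48 weeks: 0.15 × 24/48 = 7.5% at 48 weeks; 0.15 × (156 − 24)/156 = 12.7% at 3 years.
- 15% in total, stops at week 12: 0.15 × (156 − 12)/156 = 13.8% at 3 years.
- Constant hazard of 15% per 48 weeks: λ = −ln(0.85)/48 and f = 1 − (1 − e^(−λT))/(λT). This gives 7.7% at 48 weeks, 15.7% at 104 weeks and 22.3% at 156 weeks.

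**Step 2: rates under the on-study rule.** Let c be the share of placebo off-drug time spent on commercial OCA, and let off-drug OCA patients return to r0.
- OCA arm: (1 − f)r1 + f·r0
- Placebo arm: (1 − f)r0 + f[(1 − c)r0 + c·r1]
- Difference: (r1 − r0)(1 − f − fc)

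The fraction of the difference kept is therefore 1 − f when c = 0 and 1 − 2f when c = 1, whatever r0 and r1 are.

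| f | OCA | Placebo, c = 0 | Ratio; difference (kept) | Placebo, c = 1 | Ratio; difference (kept) |
|---|---|---|---|---|---|
| 7.5% | 77.0 | 40.0 | 1.925; 37.0 (92.5%) | 43.0 | 1.79; 34.0 (85%) |
| 14% | 74.4 | 40.0 | 1.86; 34.4 (86%) | 45.6 | 1.63; 28.8 (72%) |
| 22.5% | 71.0 | 40.0 | 1.775; 31.0 (77.5%) | 49.0 | 1.45; 22.0 (55%) |

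**Step 3: cases that behave differently.**
- Symptoms persist fully after OCA is stopped, or OCA-arm stoppers take commercial OCA and placebo stoppers do not: 80 against 40, ratio 2.00, no loss.
- All off-drug time in both arms is on commercial OCA: 80 against 43.0, 45.6 and 49.0, so ratios of 1.86, 1.75 and 1.63.

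**Step 4: would changing only the denominator help?** At f = 14% and c = 0, 74.4/0.86 = 86.5 and 40/0.86 = 46.5. The difference returns to 40, but both rates are inflated and the ratio stays at 1.86. Numerator and denominator must stop at the same date.

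**Step 5: censoring.** If completion or discontinuation refers to the study, the rule is close to last contact and little changes. If it refers to the drug, the graded pruritus endpoints have a shorter risk period than any pruritus. There is then a second fault: the rule applies only to patients who never report the event. A patient who stops and later has the event stays in as an event, while one who stops and has none is censored at stopping. Censoring would then depend on what happens later.

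**The case against.** The on-study rate is internally consistent. Numerator and denominator cover the same period, the text labels it as per time on study, and it is a legitimate treatment-policy summary by randomized arm. An on-treatment window has its own bias: if pruritus causes stopping, cutting at the last dose is informative. Both points stand, and they are why the on-study rate should not be replaced.

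Other views of the same question exist: TEAEs by relatedness and TEAEs leading to withdrawal (Section 15.4.1), new-or-worsened pruritus (Section 15.4.3), and the pruritus VAS and PBC-40 itch domain (Section 13.2.6). They soften the gap, but none is a rate per time on treatment.

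Follow-up after stopping will also be incomplete. Section 8.4 only encourages it, consent may be withdrawn, transplanted patients leave the visit schedule (Section 8.4.2), and later enrollees have less than 3 years. The longer-horizon shares above are therefore towards the high end for a 15% rate.

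Three stronger readings are tempting, and the documents do not support them:
- **The missing TEAE closing date is a defect in itself.** A cut-off of that kind is commonly fixed in the SAP, which is not shown. It matters here only because the denominator is already written down.
- **The safety contrast is bound to shrink.** Step 3 shows cases with no loss, and no document gives off-drug symptom rates or commercial-OCA uptake.
- **The rate ratio is understated by 13% to 24%.** That needs 30–40% stopping on OCA against 15% on placebo, at about six months, with 2 to 3 years of follow-up and no event-days at all off drug. The first is not in the protocol, and the last is implausible for symptoms whose baseline severity is recorded as part of the disease history. At 15% in both arms, the same formula gives 0.888/0.888 = 1, so no change in the ratio.

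**Conclusion.** The point holds as a gap in what is specified, not as a demonstrated bias. Off-drug and commercial-OCA time and events are credited to the randomized arm, and no on-treatment rate accompanies that summary for a primary safety objective.

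The expected direction is towards a smaller difference. If the 15% applies per 48 weeks and off-drug OCA patients return to the placebo rate, the loss is about 7.5% of the difference over 48 weeks and up to about 22% over 3 years. If all placebo off-drug time is on commercial OCA and stopping is equal in the arms, the loss doubles: about 15% and up to 45%. If symptoms persist, or only OCA-arm stoppers take commercial OCA, it is nil. Mandated interruptions for liver chemistry (Section 8.4.1.2) would add off-drug time that is not counted here.

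The censoring inconsistency is certain as a matter of wording. Its effect depends on whether discontinuation means drug or study. No formal test or decision rule is affected.

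**What to change.** - Keep the on-study event-day rate as written.
- Add an on-treatment rate for pruritus and fatigue, with numerator and denominator both ending at last dose plus a stated window (for example 30 days) or at first commercial OCA, whichever is earlier. State whether interruption time counts.
- Use one defined censoring date for all six time-to-onset analyses, applied alike to patients with and without a later event. If discontinuation is kept in the wording, say whether it means drug or study.
- Show events after the start of commercial OCA separately, by randomized arm.

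The cost is a wording change and one extra table set from data already collected; nothing in clinical management changes. Because truncation at the last dose may be informative, the on-treatment rate should be read alongside the on-study rate and not in its place.

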15.5. Efficacy Analyses

This study does not plan to test a formal hypothesis for any efficacy endpoint.

The endpoints of efficacy assessments are change in total and direct bilirubin, INR, creatinine, albumin, platelets, ALP, ALT, AST, and GGT from baseline to Week 48 (end of the study), change from baseline to Week 48 in CP score and components of the CP score, and change from baseline to Week 48 in MELD and components of the MELD score. Analyses of change from Baseline to Week 48 (end of study) will be modelled between treatment groups using ANCOVA model with change from Baseline as the dependent variable, treatment group and randomization stratification factor as fixed effects and the baseline value as a covariate. The same analysis will be carried out using percentage change from Baseline as the dependent variable.

Analyses of change from Baseline to Week 48 (end of study) will be modelled between treatment groups using ANCOVA model with change from Baseline as the dependent variable, treatment group and randomization stratification factor as fixed effects and the baseline value as a covariate. The same analysis will be carried out using percentage change from Baseline as the dependent variable.

Summary statistics of the laboratory values will be provided by treatment group. The results, change from Baseline, and percentage change from Baseline values, as well as estimates of least-square (LS) means, standard errors (StdErr), and 2-sided 95% CIs, will be presented by treatment group. Estimates of the mean difference between treatment groups, the StdErr of the difference, and 2-sided 95% CI of the difference will also be presented.

Risk Scores: Changes from baseline in the MELD score and in CP score will be summarized and analyzed using the Wilcoxon Rank Sum Test. The median differences and 95% CI of the median differences between treatment groups will be constructed using Hodges-Lehmann estimate. If the median differences between treatments are not symmetrical around the median, the Sign Test may be used.

Shifts in MELD scores from Baseline will be reported by visit using the following categories: <10, 10 to <12, 12 to <13, 13 to <14, 14 to <15, and ≥ 15 .

CP class will be presented in shift tables showing the shift from baseline to each scheduled post-baseline visit by the count and percentage of patients within each shift classification.

Individual factors will be presented in a listing.

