9.4. Randomization and Blinding

9.4.1. Methods of Assigning Patients to Treatment Groups

This study will be conducted in a double-blind, placebo-controlled manner. Enrolled patients who meet all eligibility requirements will be randomized in a 1:1 ratio to one of two treatment groups: placebo or OCA based on a predefined randomization code (generated by Sponsor or designee) using an interactive web response system (IWRS), which the Sponsor intends will serve as a computer-based patient registration system at Screening and Day 1.

Randomization will be stratified by CP class (CP-B or CP-C). Baseline MELD scores will be monitored on an ongoing basis to ensure adequate distribution of MELD scores. The IWRS will serve as the investigational product inventory and management system and may be integrated with the study database.

The Investigator or designee will be required to register the patient in the IWRS and may be prompted to provide patient data necessary to properly randomize and allocate the patient to treatment. A randomization number will be assigned and investigational product (OCA or placebo) dispensing information will be provided (eg, bottle numbers allocated) while maintaining the study blind.

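### The Sign Test offered as fallback for comparing MELD and Child-Pugh change between arms is a one-sample or paired test and cannot make that comparison

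*Protocol*

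**What the plan says.** The current protocol (Version 2), section 15.5, handles these two scores in two ways.

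- **ANCOVA.** The Week 48 efficacy endpoints listed there include "change from baseline to Week 48 in MELD and components of the MELD score". The CP score and its components are listed in the same way. All are modelled with "treatment group and randomization stratification factor as fixed effects and the baseline value as a covariate". The stratum is CP class, B or C (section 9.4.1). The synopsis gives ANCOVA only.
- **Rank analysis.** The Risk Scores paragraph says: "Changes from baseline in the MELD score and in CP score will be summarized and analyzed using the Wilcoxon Rank Sum Test". It continues: "The median differences and 95% CI of the median differences between treatment groups will be constructed using Hodges-Lehmann estimate". Then comes the fallback: "If the median differences between treatments are not symmetrical around the median, the Sign Test may be used". No stratification is stated for this analysis.

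The section does not say which of the two leads. It states that no efficacy hypothesis is formally tested. The opening of section 15 commits instead to summary statistics and 95% confidence intervals for the contrast between the arms.

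**The concern.** A sign test counts how many differences are positive, within matched pairs or against a fixed value. Allocation here is 1:1 to two parallel arms with no matching, so the test has nothing between arms to count. The condition that triggers it comes from a different procedure, and the word *may* leaves the switch to be decided after the data are seen.

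An analyst following the sentence would have to abandon it or run a sign test inside each arm and set the two p-values side by side. The second course answers whether each arm changed from baseline, whereas the secondary objective (section 6.2) is the effect of OCA compared with placebo. An SAP written to follow the protocol would inherit the error.

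**Working it through.** **Setting.** Section 15.2 gives 20 + 10 + 20 = 50 patients, at least 20% of them CP-C. With 1:1 allocation that is 50/2 = 25 per arm. The minimum CP-C count is 0.20 × 50 = 10, so about 5 CP-C and 20 CP-B per arm. The protocol gives no figure for the MELD/CP comparison itself, so there is none to reproduce.

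**Step 1: what a sign test could be applied to.**

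- *OCA–placebo pairs.* None exist.
- *All OCA-minus-placebo differences*, the set whose median is the Hodges-Lehmann estimate. There are 25 × 25 = 625. The number that are positive is the Mann-Whitney count, which is the rank sum test already planned. A sign test would treat the 625 as independent, with variance 625/4 = 156.25. The null variance of the count, without ties, is 25 × 25 × 51/12 = 2656.25, which is 17 times larger. The nominal 1.96 cut-off then lies only 1.96/√17 = 0.475 true standard errors from the null, giving about 63% false positives.
- *Each patient's change, within an arm.* This is computable, but it tests change from baseline in that arm.

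**Step 2: the within-arm reading, simulated with no treatment effect.** Assumptions not in the documents: whole-point changes, SD 3 points, the same mean drift in both arms, CP-C mean change 0, 2 or 4 points above CP-B, two-sided 5%, 3000 runs per setting.

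| Drift | CP gap | Significant, OCA | Significant, placebo | Arms disagree |
|---|---|---|---|---|
| 1 | 0 | 20.7% | 19.9% | 32.6% |
| 1 | 2 | 35.7% | 35.1% | 47.6% |
| 1 | 4 | 45.2% | 46.0% | 50.1% |
| 2 | 0 | 67.8% | 71.6% | 41.9% |
| 2 | 2 | 82.9% | 82.1% | 29.0% |
| 2 | 4 | 87.1% | 87.6% | 22.2% |

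Disagreement between arms could be misread as a treatment effect. Here it arises with none.

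**Step 3: the trigger.** The rank sum test is valid when both arms share one distribution, symmetric or not. The Hodges-Lehmann estimate is read as a shift when the arms have the same shape, again with no need for symmetry. Asymmetry is therefore no reason to leave either.

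**Step 4: the promised output.** The within-arm sign test yields no difference between arms and no interval for one.

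**Step 5: stratifying the rank analysis.** The same simulation compared the unstratified Wilcoxon with the van Elteren test (Wilcoxon stratified by CP class).

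- *No treatment effect* (drift 0, 1, 2; gap 0, 2, 4): rejection was 3.2–5.2% unstratified and 4.4–5.8% stratified. The simulation standard error is √(0.05 × 0.95/3000) = 0.4 points.
- *2-point treatment effect* (range over the three drifts):

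| CP gap | Unstratified | Stratified | Loss without stratum |
|---|---|---|---|
| 0 | 60.8–61.3% | 60.1–60.5% | none |
| 2 | 58.2–58.8% | 60.1–60.8% | about 2 points |
| 4 | 50.1–51.2% | 58.9–60.8% | about 9–10 points |

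Leaving out the stratum does not inflate false positives. It can cost precision.

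**The case against.** The strongest reply is that little hangs on the sentence. No p-value carries a decision. The fallback is optional. The Hodges-Lehmann interval and the ANCOVA difference are planned in their own right. PK and safety are the primary objectives, and the order of the secondary objectives implies no ranking. All of this stands and limits the weight of the point, but it does not make the sentence correct.

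It could also be said that a two-sample median test was meant. The protocol does not name one, and none is needed, because asymmetry does not disqualify the rank sum test.

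A reader might infer three stronger points that the documents do not support:

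- *That MELD and CP change rest on an unstratified test alone, or that such a test is invalid.* Section 15.5 and the synopsis also plan an ANCOVA with the CP stratum and the baseline value, and the unstratified test kept its level in Step 5. The SAP may specify stratification.
- *That the rank analysis ought to lead.* Nothing in the protocol ranks it above the ANCOVA, which already adjusts for stratum and baseline.
- *That the MELD shift categories, with a single class from 15 upwards, hide worsening.* That is one descriptive table. A rise above 15 still enters the ANCOVA, the rank analysis and the summaries, and the cut at 15 matches the protocol's own MELD event in section 15.6.

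**Conclusion.** The Sign Test sentence is wrong as written, and this rests on no numerical assumption: the test does not fit the design, the trigger belongs to another procedure, and the result would not be the between-arm estimate that section 15 promises. The simulated percentages only illustrate how misleading a within-arm substitute could be. They depend on the assumed SD, drift and CP gap.

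Stratifying the rank analysis is a refinement, not the repair of an invalid test. Its gain of about 0–10 points of power rests on an assumed gap of 0–4 points between CP classes in mean change, and the protocol gives no such figure.

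That two analyses of the same change are planned without an order between them is a gap in section 15.5, since one estimates a mean difference and the other a median shift. Overall this is a clear error with limited consequence, worth correcting because correction is nearly free.

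**What to change.** 1. Delete the Sign Test sentence from section 15.5 and keep the Wilcoxon and Hodges-Lehmann analysis whether or not the differences look symmetric.
2. State which analysis leads for change in MELD and CP score, the ANCOVA or the rank analysis. The choice is the sponsor's, made before unblinding.
3. As an inexpensive refinement, stratify the rank analysis by randomized CP class (van Elteren test with a stratified Hodges-Lehmann estimate and 95% interval). This matches the ANCOVA in section 15.5 and the log-rank and Cox analyses in section 15.6.

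The cost is wording in the protocol or SAP and a small programming change for item 3. No new data or patients are needed.
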